4.9.5. Mini-Mental State Exam (MMSE)

MMSE was collected based on earlier versions of 233AS102 Protocols and then removed from Protocol Amendment V6.0. All collected data will be still summarized for final analysis. Summary statistics for actual values and change from baseline of the total score of MMSE will be presented for each visit by study group. When there are multiple assessments during a single visit, the minimal value will be taken as the value for that visit. A listing of MMSE data for individual patients will also be provided.

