2.3. Protocol Amendments

During the course of study conduct, protocol amendments were developed for Study 233AS102. Due to the changes of the assessments (e.g. adding assessments to align with Study 233AS101 amendment, removing assessments to minimize burdens on the subjects, changes of assessment frequency, etc.), the collected assessments and frequency may vary among subjects enrolled from Part A/B and Part C. Part C subjects started enrolling in Study 233AS102 at protocol amendment V4.0, thus the assessments changes in protocol amendment V4.0 or prior will have no impact on Part C subjects. The new assessments introduced in protocol amendment 4.0 or later (i.e. ventilation use, [REDACTED]) will only be collected part of the way through the study for Parts A and B subjects. [Table 2](#) below summarized the changes for the impacted endpoints.

MMSE was removed from the protocol amendment V6.0; however, we will include summaries for all the data collected.

Table 2: Summary of changes in protocol amendments

Endpoint	V3.0	V4.0	V5.0	V6.0
Neurological examination (excluding MMSE)	Changed to limited neurological examination (cranial nerves, coordination/cerebellar function, reflexes, motor)	Added post-dose timepoints	Removed cranial nerves examination	Removed from all dosing visits (except for pre-dose baseline)
MMSE		Added post-dose timepoints	Reduced from every 4 weeks to every 12 weeks prior to week 48, and to every 24 weeks up to week 216.	Removed
ECG				Removed from all dosing visits (except for pre-dose baseline)
Vital sign		Added post-dose timepoints		
Immunogenicity, PK		Decreased from 4 weeks to 8 weeks		
ALSFRS-R		Added Day 15		

SVC				Reduced from every 4 weeks to every 12 weeks
HHD		Added Day 15		Reduced from every 4 weeks to every 12 weeks
Ventilation use, [REDACTED]		Added		

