3.1. Dates and Points of Reference

- Study Day 1: the date of the first dose of study treatment in 233AS102
- Study Day
 - For a date on or after Study Day 1
$$\text{Study Day} = (\text{Date of Interest}) - (\text{Study Day 1}) + 1$$
 - For a date before Study Day 1
$$\text{Study Day} = (\text{Date of Interest}) - (\text{Study Day 1})$$
- Unless stated otherwise, baseline data are defined as the data collected prior to the time and/or on the date of first dose, which is usually the same day as the Day1/Baseline visit in 233AS102. If there is more than one value on/before the date of the first dose, the non-missing value closest to and prior to the first dose will be used as the baseline value
- *Visit window for analysis*

If, due to the COVID-19 pandemic, subjects could not attend clinic visits during protocol defined visit windows, they were given some allowance to have a delayed visit. There may also have been subjects who attended visits outside of the protocol defined windows for other reasons. Regardless of whether the delayed visit was due to the COVID-19 pandemic or not, these are recorded under scheduled visits and are also considered to be protocol deviations. Visit windows will not be applied to scheduled visits for analysis purposes. If a subject had a phone visit followed by a delayed clinic visit, the clinic visit is still recorded as the scheduled visit. The scheduled visit will always take precedence over unscheduled visits.

For subjects who are early terminated (ET), EOS visit is defined as the scheduled follow-up visit 4 weeks after last dose. Data from early withdrawal visits and post

baseline unscheduled assessments will be assigned to an appropriate scheduled post baseline visit using a windowing scheme for assessments that are tabulated or summarized by visit. Scheduled visits will not be windowed.
The visit windowing for endpoints is given in the table below:

Table 3 Visit Windows for Safety Endpoints and CSF PK Endpoints

Visit	Safety Endpoints and CSF PK Concentration*		
	Lower Bound (Day)	Upper Bound (Day)	Target Day
Week 2 (Day 15)	8	21	15
Week 4 (Day 29)	22	42	29
Week 8	43	70	57
Week 12	71	98	85
Week 16	99	126	113
Week 20	127	154	141
Week 24	155	182	169
Week 28	183	210	197
...
Week 352	2451	2478	2465
Week 356	2479	2506	2493
Week 360	2507	2534	2521
Week 364	2535	2562	2549

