* This windowing covers the following endpoints: PK CSF concentration and safety endpoints: vital signs (temperature, blood pressure, pulse rate, respiratory rate), clinical laboratory tests (Hematology, Coagulation, Chemistry, and Urinalysis), pregnancy test, neurological examinations, C-SSRS, [REDACTED], ECG.

Note: ECG will not be collected at Week 2.

Table 4 Visit Windows for MMSE

Visit	MMSE *		
	Lower Bound (Day)	Upper Bound (Day)	Target Day

Week 12	71	98	85
Week 24	155	182	169
Week 36	239	266	253
Week 48	323	350	337
Week 72	491	518	505
Week 96	659	686	673
... (every 24 weeks)
Week 340	2367	2394	2381
Week 364	2535	2562	2549

* This windowing covers the safety endpoint: MMSE. To be performed at Week 12, 24, 36, and 48 Visits (i.e., every 12 weeks); Week 72, 96, 120, 144, 168, 192, and 216 Visits (i.e., every 24 weeks); and Week 228 Visit under Protocol V5. MMSE assessment is removed in Protocol V6.

**For MMSE, there are some subjects who also have assessments during Screening, Day 1, Week 2, Week 4, Week 8, etc. (i.e. every 4 weeks) under Protocol V3 and Protocol V4. For part C subjects, follow [Table 3](#) for windowing up to and including Week 24. For part A/B subjects, follow [Table 3](#) for windowing up to and including Week 120. All visits up to Week 12 will be summarized for all subjects.

Table 5 Visit Windows for PK Concentration in Blood/Immunogenicity Endpoints

	PK/Immunogenicity Endpoints *		
Visit	Lower Bound (Day)	Upper Bound (Day)	Target Day
Week 12	71	98	85
Week 20	127	154	141
Week 28	183	210	197
... (every 8 weeks)
Week 356	2479	2506	2493
Week 364	2535	2562	2549

* This windowing covers the following safety endpoints: blood samples for PK, and blood samples for plasma anti-tofersen Ab. ,

Considering the high frequency of postbaseline visits and the relatively small gap between adjacent visits, the lower bound and the upper bound for the visit windows are based on the midpoints of the scheduled visits. The date of first dose will be the reference point (Day 1).

- If more than one observation is within the same window, data from the protocol-specified scheduled visit will be used for that visit.
- If neither of the observations are from a protocol-specified scheduled visit the observation closest to the planned target date will be used. However, if both the observations are equidistant from the target date, the latest one will be used; if repeated measurements are on the same day, then the last measurement will be used.

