- If there is more than one observation in a window for a dosing visit (Day 15 to Week 360 visits), the observation on the day of dosing will be chosen over the observation where dosing did not occur on the same day.
- Some of the safety assessments are collected postdose in addition to the predose assessments (e.g. vital signs at Day 15 to Week 360 visits). When windowing any predose assessments these should be the last available assessment prior to the dose. When windowing any postdose assessments they should correspond to the same dose as the predose assessment used for that visit. These summaries will present predose and postdose separately on by-visit summaries. If one of these assessments is collected at an unscheduled visit where there is no dosing, the assessment will be assigned as a predose assessment. Additionally, the protocol for 233AS102 initially collected some assessments (e.g. vital signs) only pre-dose, therefore these assessments will be summarized under pre-dose. For Part C subjects, the pre-dose assessment may need to be taken from Day 197 visit of 233AS101.

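### MMSE change from baseline compares the lower of two tests at a visit with a single predose baseline, so the mean is shifted downward even if nobody declines

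*SAP*

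**What the plan says.** SAP Section 4.9.5 keeps all collected MMSE data in the final analysis, although protocol Version 6 dropped the test. It plans this output: "Summary statistics for actual values and change from baseline of the total score of MMSE will be presented for each visit by study group". For visits with more than one test it adds: "When there are multiple assessments during a single visit, the minimal value will be taken as the value for that visit".

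Section 4.9.5 defines no MMSE baseline, so the general definition in Section 3.1 applies: where several values exist, "the non-missing value closest to and prior to the first dose will be used as the baseline value". That is one predose value.

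Table 2 in Section 2.3 records for the MMSE at protocol Version 4: "Added post-dose timepoints".

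Section 3.1 also has a general rule. It begins "Some of the safety assessments are collected postdose in addition to the predose assessments", gives vital signs as an example, and goes on: "These summaries will present predose and postdose separately on by-visit summaries". The footnote to Table 4 classes the MMSE among the safety endpoints: "This windowing covers the safety endpoint: MMSE".

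**The concern.** The two sides of the subtraction are built differently. The visit side is the lower of two readings and the baseline side is one reading. The lower of two noisy readings lies on average below a single reading, so the difference is negative before any real change occurs.

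The second reading comes after a lumbar puncture, for which protocol Section 11.1.3 allows anesthesia or sedation. Merging it with the predose reading also hides whether a low score was there before the dose or appeared after it.

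At stake is the reading of the cognitive safety table. It could suggest a decline that the derivation produced, and it could not separate a short-lived postdose effect from a lasting one.

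**Working it through.** **Inputs from the documents.** The minimum rule is in SAP 4.9.5 and the single predose baseline in SAP 3.1. Postdose MMSE from Version 4 is in SAP Table 2. The 30-point range comes from the Version 3 amendment summary and is used only for the ceiling. The Version 4 and 5 schedules in the amendment summaries are used only as evidence of what was collected. They mark the MMSE predose and postdose at dosing visits where it was given, and once at the final visit (under Version 4 also once at follow-up visits).

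**Inputs assumed.** The documents give no MMSE SD, mean or test-retest correlation. I take a within-person SD *s* of 0.5 to 2 points.

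**There is no plan figure to reproduce.** The SAP states no expected change, SD or power for the MMSE.

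**Step 1, closed form.** Let the true score be T, unchanged. Baseline = T + e0 and visit value = min(T + e1, T + e2). The errors are normal with mean 0 and SD *s*, and e1 and e2 have correlation ρ. Then

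E[change] = -s × √((1 - ρ)/π).

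| ρ | √((1 - ρ)/π) | Expected change |
|---|---|---|
| 0 | √(1/3.1416) | -0.56 s |
| 0.5 | √(0.5/3.1416) | -0.40 s |
| 0.8 | √(0.2/3.1416) | -0.25 s |

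**Step 2, in points, with the ceiling.** The closed form at ρ = 0 was compared with a simulation of 400,000 subjects per setting: integer scores, true and observed scores capped at 30, between-person SD 1.5, no true change.

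| s (points) | Closed form | Mean 28, capped | Mean 29, capped |
|---|---|---|---|
| 0.5 | -0.28 | -0.26 | -0.23 |
| 1 | -0.56 | -0.51 | -0.45 |
| 1.5 | -0.85 | -0.73 | -0.63 |
| 2 | -1.13 | -0.91 | -0.81 |

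In the same simulations, predose against predose baseline gave changes between -0.01 and +0.01 points.

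**Step 3, effect on individuals.** At s = 1 and mean 28, an apparent fall of 2 or more points occurs in 12.9% of subjects with predose against predose, and in 21.2% with the minimum. Any fall occurs in 34.3% and 49.9% respectively.

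**Step 4, where it arises.** Only a visit with more than one test is affected. Parts A and B visits before Version 4 had no postdose test, and final visits under Versions 4 and 5 had one test. A table row that mixes the two kinds of subject carries the shift in proportion to the share p with two tests: p × (-0.56 s). At s = 1 and p = 0.5 this is 0.5 × (-0.56) = -0.28 points.

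**The case against.** **A worst-value rule can be deliberate.** Taking the lowest score errs toward showing harm and can catch acute worsening after intrathecal dosing. A lower postdose score may be real, which a calculation with no true change leaves out. This stands as a reason to show a worst value somewhere. It does not justify an unmatched baseline in a mean-change table. Elsewhere the SAP keeps extremes apart: Section 4.9.4 reports maximum QTcF increases as labelled categories beside the ordinary by-visit change.

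**A specific rule may depart from a general one.** A reader might infer that Section 4.9.5 flatly contradicts Section 3.1. The documents do not go that far. The Section 3.1 rule does not name the MMSE, and the SAP uses endpoint-specific rules elsewhere: laboratory data take the earliest sample, while for same-day repeats from unscheduled visits Section 3.1 says "if repeated measurements are on the same day, then the last measurement will be used". What stands is that the wording of Section 3.1 covers the MMSE and Section 4.9.5 does not say that it takes precedence. If the minimum was meant only for repeats within one timepoint, the conflict would disappear, but the text does not say so.

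**A drop at the switch to 100 mg.** Because Version 4 both added postdose tests and moved remaining subjects to 100 mg, a reader might expect a visible fall at the dose change. The planned tables would not show one. They run by visit, and Table 6 pools Parts A and B regardless of dose. Version 4 reached these subjects at different study weeks, and under Version 3 some were already assigned to 100 mg.

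**The consequence is small.** This is right. The affected visits are those under Versions 4 and 5. Version 5 reduced the MMSE to every 12 and then every 24 weeks. The two Part C groups entered under the same schedule, so their contrast is not systematically favoured. Individual MMSE data will be listed. The primary endpoint is AEs and SAEs.

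**Conclusion.** The point holds for the by-visit mean change in MMSE. The direction is certain whenever the two tests at a visit can differ and their expected score equals that at baseline. The size is not known from the documents. It is -0.56 SD with independent errors, falling to -0.25 SD at correlation 0.8. In points, with independent errors, it is about -0.3 to -1.1 for an assumed SD of 0.5 to 2, and about -0.2 to -0.8 once the ceiling is applied at a mean of 29. The larger figures assume the largest SD and no ceiling.

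Because the shift appears only where two tests were done, it also distorts comparisons over time and between Parts A/B and Part C. It does not touch the primary endpoint or any formal test. This is a worthwhile, cheap improvement to a descriptive safety table.

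**What to change.** In Section 4.9.5, summarise predose MMSE against the predose baseline, and postdose MMSE in separate rows against that same baseline, in line with Section 3.1. Keep a minimum-value summary only as a supplementary table labelled *worst value at visit*. State which value is used when a test is repeated within one timepoint, and state how Section 4.9.5 relates to the general rule in Section 3.1.

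The cost is a short text change, one extra derivation and a somewhat larger table. No new data are needed. With few subjects at some visits the postdose rows will be sparse, but they will show what was measured and when.

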4.9.6. Limited neurological examinations

The number and percentages of the status in each assessment of coordination/cerebellar function and each assessment of reflexes will be summarized by study group and visit. The reflexes neurological examination of upper and lower extremities will be analyzed as continuous variables (0 = absent, 1 = trace, 2 = normal, 3 = brisk, 4 = clonus). The descriptive statistics will be summarized by study group and visit.

The motor neurological examination will be analyzed as continuous variable (0 = no contraction or can't position limb; 1 = flicker or trace contraction, no movement; 2 = movement only with gravity eliminated; 3 = movement against gravity; 4 = movement against gravity and resistance; 5 = normal strength). Summary statistics will be presented by study group and visit.

The Ashworth spasticity scale will also be analyzed as continuous variable (1 = normal; 2 = slight increase in tone; 3 = more marked increase in tone; 4 = considerable increase in tone; 5 = affected part rigid, immobile). Summary statistics will be presented by study group and visit.

The number and percentages of the status in each assessment of general neurological examination will be summarized by study group and visit. El Escorial data will be listed.

Baseline values will be taken from Day 1 pre-dose unless an entire section of the neurological exam (i.e. coordination/cerebellar function, reflexes, motor) is missing or not done, in which case for that specific section baseline will be taken from the Screening visit for all items within that section of the exam.

Listings will also be provided with complete details for the neurological examinations.

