16.6.2.5. Limited Neurological Examinations

The changes from baseline in the limited neurological examination (coordination/cerebellar function, reflexes, and motor system) will be summarized by visit.

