4.1. General Principles

- Descriptive summary statistics will be presented for all analyzed endpoints. Unless otherwise specified, for continuous endpoints, the summary statistics will generally include number of subjects with data, mean, standard deviation, median, 25th percentile, 75th percentile, minimum and maximum. For categorical endpoints, the summary statistics will generally include number of subjects with data, and the percentage of those with data in each category.
- All summaries and listings will be presented by study group and additionally by prior treatment group for Part C subjects unless otherwise specified. Visits in listings will be displayed as per CRF data collection rather than analysis visits.
- Listings will indicate treatment sequence, considering that subjects from Part A and B may have received different doses within 233AS102. Treatment sequence will also include prior treatment during 233AS101. Dose will also be shown where relevant e.g. dose at onset of AE in AE listings.
- The statistical software, SAS®(Version 9.4) will be used for all summaries and statistical analyses.

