- AEs which led to discontinuation of study drug by primary SOC and MedDRA preferred term
- AEs which led to withdrawal from study by primary SOC and MedDRA preferred term
- AEs which led to drug interrupted by primary SOC and MedDRA preferred term
- AEs which led to hospitalization by primary SOC and MedDRA preferred term (showing number and percentage of subjects with at least one occurrence in that SOC or preferred term, as well as total number of events). Further summaries of hospitalization data are also included later in this section.
- AEs that led to death
- AEs of note (serious neurologic events, falls, CSF laboratory abnormalities) for which preferred terms will be based on a medical review before final analysis and unblinding. This summary will include number and percentage of subjects with at least one event and total number of events. The follow-up adjusted incidence rates based on number of subjects as well as number of events will also be presented in the same table. If any of these are defined based on more than one preferred term, the preferred terms will also be broken down under the overall category.

The sorting order for AE incidence tables, unless otherwise specified, will be by decreasing frequency order of “Total tofersen all doses” column. For the AE summary by primary system organ class and preferred term, subjects will be counted only once within each primary SOC/MedDRA preferred term. For the summary of AEs by maximum CTCAE grade, primary system organ class and preferred term, subjects will be counted only once within each primary SOC/MedDRA preferred term and will only be counted under the maximum CTCAE grade. For the summary of related AEs, if the relationship is missing then this will be summarized as unknown.

For AEs that occurred within 24 hours of dosing, if time of AE is missing and the event occurs on the same day as the day for dosing or the day following dosing, the AE will be counted as occurring within 24 hours of dosing.

An overall summary of AEs will also be presented. A separate table will also be presented to show an overall summary of COVID-19 pandemic related AEs.

Listings of the following events will be produced.

- AEs which led to discontinuation of study drug
- AEs which led to withdrawal from study
- AEs which led to drug interrupted
- AEs related to lumbar puncture
- AEs which led to hospitalization
- SAEs
- AEs

A listing of deaths will be provided if applicable.

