4.9.4. ECG

The ECG test includes heart rate, PR interval, QRS interval, QT interval, QTc interval using Bazett's formula, QTc interval using Fridericia's formula, and RR interval.

Summary statistics for actual values and change from baseline in each ECG parameter will be presented by study group and visit.

The number and percentage of subjects with shifts from normal to each of the categorical values denoting an abnormal scan (abnormal not AE, abnormal AE) will be summarized by study group. A listing of subjects with abnormal status in ECG will be presented.

QTc (interval using Fridericia's formula) will also be examined to determine the incidence of clinically relevant abnormalities. The number of subjects evaluated and the number of subjects with clinically relevant abnormalities will be presented. The criteria for clinically relevant post-dosing abnormalities are:

- Maximum increase from baseline QTcF > 30 to 60 ms
- Maximum increase from baseline QTcF > 60 ms
- Maximum post-baseline QTcF > 480 to 500 ms
- Maximum post-baseline QTcF > 500 ms

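### SAP 4.9.6 averages limb reflexes on a 0–4 code whose normal value is the midpoint and specifies no within-subject change, although Protocol 16.6.2.5 calls for it

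*SAP*

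**What the plan says.** SAP 4.9.6 plans two summaries of reflexes. The first is the number and percentage in each status: "each assessment of reflexes will be summarized by study group and visit". The second treats the limb reflexes numerically: "The reflexes neurological examination of upper and lower extremities will be analyzed as continuous variables", with the code "0 = absent, 1 = trace, 2 = normal, 3 = brisk, 4 = clonus" and descriptive statistics by study group and visit. For continuous endpoints SAP 4.1 lists "number of subjects with data, mean, standard deviation, median, 25th percentile, 75th percentile, minimum and maximum". SAP 4.9.6 also defines a baseline (Day 1 pre-dose, or Screening if a whole section of the examination is missing) and ends: "Listings will also be provided with complete details for the neurological examinations".

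Protocol 16.6.2.5 asks for something more: "The changes from baseline in the limited neurological examination (coordination/cerebellar function, reflexes, and motor system) will be summarized by visit". SAP 4.9.6 names no change or shift summary. SAP Section 5, which lists departures from the protocol's analyses, does not mention the omission.

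**The concern.** A mean can be read for safety when a scale has a good end and a bad end. The motor grade (0–5) and the Ashworth scale (1–5) in the same section do; the reflex code does not. Normal lies in the middle and both ends are abnormal, so the mean, or a mean change, has no fixed safety direction.

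The status counts help only in part. It is unclear whether they include the 0–4 limb grades or only other reflex items. Even if they do, they describe the group at each visit and do not follow a subject from baseline. Under protocol version 6 the examination is scheduled only at Screening, Day 1 and the Final or Early Termination Visit, and otherwise takes place at the investigator's discretion. Counts at different visits may therefore come from different subjects.

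What is at stake is the readability of one neurological safety summary in a study whose primary objective is long-term safety and whose final standalone analysis focuses on safety and exposure.

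**Working it through.** The documents give no reflex data and no figure to reproduce. The distributions below are assumptions, each with 100 subjects scored on the SAP's code. They show what the SAP 4.1 statistics can and cannot reveal.

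**Step 1: the planned statistics at one visit.** Mean = sum of (score × count) / 100. For 20 absent, 60 normal and 20 clonus: (20×0 + 60×2 + 20×4)/100 = 2.00. SD = √(40×2²/99) = 1.27.

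| Assumed group of 100 | Mean | SD | Median | Q1–Q3 | Range | Not normal |
|---|---|---|---|---|---|---|
| All normal | 2.00 | 0.00 | 2 | 2–2 | 2–2 | 0% |
| 10 absent, 10 clonus, 80 normal | 2.00 | 0.90 | 2 | 2–2 | 0–4 | 20% |
| 20 absent, 20 clonus, 60 normal | 2.00 | 1.27 | 2 | 2–2 | 0–4 | 40% |
| 30 trace, 30 brisk, 40 normal | 2.00 | 0.78 | 2 | 1–3 | 1–3 | 60% |
| 20 absent, 10 clonus, 70 normal | 1.80 | 1.08 | 2 | 2–2 | 0–4 | 30% |
| 20 absent, 80 normal | 1.60 | 0.80 | 2 | 2–2 | 0–2 | 20% |

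In the first four rows the mean and median are identical. The SD and range separate the abnormal groups from the all-normal one, and in the fourth row the quartiles do too. In the last two rows the changes do not balance, and the mean moves.

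**Step 2: a non-normal start.** If all 100 begin at brisk, the mean is 3.00. If 33 then lose the reflex, the mean is (33×0 + 67×3)/100 = 2.01. That resembles normalisation, yet no subject scores 2. The median stays at 3 and the range becomes 0–3.

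**Step 3: what marginal counts miss.** Start with 80 at normal and 20 at brisk. Let 20 go from 2 to 3 and the other 20 go from 3 to 2. The counts are 80 and 20 before and after, the mean is (80×2 + 20×3)/100 = 2.20 at both times, and the mean change is 0. A shift table counts 20 of the 80 subjects at risk of becoming increased: 20/80 = 25%.

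**Step 4: the plan's neighbouring sections.** SAP 4.9.2 (laboratory), 4.9.3 (vital signs), 4.9.4 (ECG) and 4.9.5 (MMSE) all name change from baseline. ECG also has a shift summary: "The number and percentage of subjects with shifts from normal to each of the categorical values denoting an abnormal scan". Laboratory values share the feature that matters here, since normal lies between two abnormal sides. SAP 4.9.2 counts shifts to low and to high separately, each among subjects who were not already in that state at baseline and had a post-baseline value. SAP 4.9.6 does neither for reflexes.

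**The case against.** The strongest reply is that the paragraph already contains the remedy. If the status counts cover the 0–4 limb grades, as a plain reading allows, every abnormal distribution in Step 1 would show in that table. The SD, quartiles and range are reported beside the mean, and every examination is listed. A reader might infer that reflex worsening would be hidden from the study's outputs, that change in either direction leaves the mean at normal, or that only the SD would react. The documents support none of these: Step 1 shows the range and sometimes the quartiles reacting, and a loss in 20% with no offsetting gain takes the mean to 1.60.

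The link to the named safety topics is also loose. The SAP's "AEs of note (serious neurologic events, falls, CSF laboratory abnormalities" are identified from preferred terms after medical review, not from reflex scores. The primary endpoint is the incidence of AEs and SAEs, and the reflex summary is descriptive support.

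Finally, the protocol's requirement covers coordination and motor as well as reflexes, and SAP 4.9.6 names no change summary for those either. That is correct. It makes the mismatch wider than reflexes rather than excusing it for them. The midpoint problem remains specific to reflexes.

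What survives is narrower: the counts are ambiguous in scope and marginal in form, and nothing specified delivers the within-subject change that the protocol calls for. Defining a baseline may imply that change tables are intended, but a mean change on this code would have the same lack of direction.

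**Conclusion.** The point holds in a limited form. The mean of the limb reflex code is a poor safety summary because normal is its midpoint, and SAP 4.9.6 specifies no within-subject change although Protocol 16.6.2.5 requires changes from baseline. Masking in the mean needs offsetting changes or a non-normal starting level; the examples show that it can happen, not that it will. Spread statistics, counts and listings limit the harm, and no primary inference is affected. The gap would be larger if the status counts exclude the limb grades, and smaller if they include them. Either way, marginal counts do not replace change from baseline. This is a modest, worthwhile improvement to a descriptive safety table.

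**What to change.** In SAP 4.9.6:

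- State that the by-visit number and percentage summary covers each 0–4 grade for every limb reflex.
- Add, for each limb reflex, a shift table from the baseline already defined there to post-baseline, in three categories: reduced (0–1), normal (2) and increased (3–4). Present it by visit, to match the protocol, and for any post-baseline value, so that discretionary examinations and those made under earlier protocol versions are kept.
- Count shifts to reduced and to increased separately, with at-risk denominators as in SAP 4.9.2.
- Do not rely on the mean, or on distance from normal (|score − 2|) alone. That distance is 1 both before and after a fall from 3 to 1, and 2 both before and after a fall from 4 to 0.
- Drop the continuous summary or keep it as secondary.

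Three categories do not separate brisk from clonus or trace from absent; the grade counts and listings cover those moves. The cost is a few sentences and one extra table, with no new data.
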